10.4.3 Secondary analyses of primary endpoint

As a sensitivity analysis, we will perform a complete-case analysis using only subjects who have non-missing outcome data in a logistic regression model adjusting for stratification variables as well as covariates that we find to be associated with missing AD status.⁷⁸ The effect of emollient use will be evaluated with a model similar to the primary analysis, but substituting an indicator of regular reported emollient use (≥ 3 days per week) for intervention allocation. In a separate model, we will include a variable for bathing frequency. In the likely case that bathing and emollient use frequency are associated, we will create and test a combined categorical variable. We will return to the primary intervention-effect model and consider additional covariates previously found or suspected to be associated with AD, such as climate, season of birth, pet ownership, bathing frequency, and characteristics of the living environment using a change-in-estimate approach.⁸³ Finally, we will compare clinic-stratified intervention effects on the primary AD outcome and test their equality with a Breslow-Day test; the purpose is to identify 'large' differences where further investigation into potential protocol deviations or other factors may be warranted, and these results will be interpreted with caution.

10.4.4 Analysis of Key Secondary Endpoints

To test the hypothesis that emollient use delays onset of AD, we will compare time to onset using child's age in months with discrete time-to-event methods.⁸⁴ Time to AD onset will be defined in two ways, as (1) parental report of age of eczema onset and (2) age at first diagnosis recorded in patient chart. Censoring will occur at the date of last parental report or last visit recorded in the patient chart. We will also compare the intervention and control groups with respect to conditions and symptoms that include the need for topical therapy, asthma, food allergy symptoms, and dichotomized disease severity measures as binary measures, sleep loss days as counts, and AD severity scores (POEM and IDQOL) as continuous measures. We will test for differences using logistic, Poisson, or linear regression, adjusting for stratification variables. The incidence of adverse events at two years of age will also be compared between the treatment and control groups with a two-tailed chi-square test at the 0.05 level of significance.

11 SOURCE DOCUMENTS AND ACCESS TO SOURCE DATA/DOCUMENTS

Study staff will maintain appropriate research records for this study, in compliance with ICH E6, Section 4.9 and regulatory and institutional requirements for the protection of confidentiality of participants. Study staff will permit authorized representatives of NIAMS and regulatory agencies to examine (and when required by applicable law, to copy) research records for the purposes of quality assurance reviews, audits, and evaluation of the study safety, progress and data validity.

12 ETHICS/PROTECTION OF HUMAN SUBJECTS

12.1 Ethical Standard

The investigator will ensure that this study is conducted in full conformity with the principles set forth in The Belmont Report: Ethical Principles and Guidelines for the Protection of Human Subjects of Research, as drafted by the US National Commission for the Protection of Human Subjects of Biomedical and Behavioral Research (April 18, 1979) and codified in 45 CFR Part 46 and/or the ICH E6.

12.2 Institutional Review Board

The protocol, informed consent form(s), recruitment materials, and all participant materials will be submitted to the IRB for review and approval. Approval of both the protocol and the consent form must be obtained before any participant is enrolled. Any amendment to the protocol will require review and approval by the IRB before the changes are implemented in the study.

12.3 Informed Consent Process

Informed consent is a process that is initiated prior to the individual agreeing to participate in the study and continues throughout study participation. A description of possible risks and benefits of study participation will be provided to families. An IRB-approved consent form describing in detail the study procedures and risks will be reviewed electronically and made available to the participant. The CCC will be available via toll-free phone number to explain the research study to the participant and answer any questions that may arise. The participant will electronically sign the informed consent document prior to any study-related assessments or procedures. Participants will be given the opportunity to discuss the study with their surrogates or think about it prior to agreeing to participate. Participants may withdraw consent at any time throughout the course of the study. An electronic copy of the signed informed consent document will be available to download and will be e-mailed to participants for their records. Participants will be informed that the quality of their clinical care will not be adversely affected if they decline to participate in this study.

The consent process will be documented in the research record.

13 DATA HANDLING AND RECORD KEEPING

13.1 Data Management Responsibilities

Data collection and accurate documentation are the responsibility of the study staff under the supervision of the investigator. All source documents and medical chart abstractions must be reviewed by the CCC and DCC staff, who will ensure that they are accurate and complete. Unanticipated problems and adverse events will be reviewed by the PI.

13.2 Data Capture Methods

Data will be collected on standardized forms on which nearly all responses have been pre-coded. Data will be collected directly from parents using web-based surveys. PBRN research coordinators will perform health record reviews of enrolled infants at 24 months and send data to the CCC to enter directly into the REDCap database. In both cases, the case report forms will serve as source documentation. The DCC will monitor for timely entry of data and maintain a study calendar.

13.3 Types of Data

The following types of data will be collected over the course of the study:

- Questionnaire responses: electronic surveys will allow parents to enter data directly into a REDCap database. If necessary, DCC staff may contact parents to answer survey questions over the phone and will enter responses into REDCap.
- Health record review: research coordinators will perform health record review at infant age 27 months to see if an AD diagnosis has been made by the primary care provider, as well as other clinical data of interest.
- Current participant contact information
- Participant contacts and contact attempts
- Emollient preference and tracking
- Participant compensation
- Safety data: Safety data will be stored in REDCap with other study data.
- Missing Data

The study's approach to missing data follows the recommendations of the National Research Council of the prevention and treatment of missing data in clinical trials.⁸³ Specifically, we will use the following methods to prevent missing data and account for it in the analyses:

- Participants will be informed at the time of consent the importance of remaining in the study and providing reasons for withdrawal if needed

- Participant retention methods including text messaging and medical record review
- Key covariates will be collected at baseline regardless of intervention arm
- Missing data are addressed in our statistical analyses using state-of-the-art procedures like multiple imputation procedures and use of sensitivity analyses

13.4 Performance Monitoring

The DCC will present regular reports to the CCC and PBRN directors. These include:

- Monthly recruitment reports: reports of the number of dyads screened, enrolled, screen-failed, and randomized by month and by PBRN, as well as average randomized per month.
- Annual committee reports: reports detailing recruitment, baseline patient characteristics, data quality, incidence of missing data and adherence to study protocol by clinical site, will be provided semi-annually to the Steering Committee.
- Semi-annual Safety Monitor reports: every report includes adverse events, patient recruitment, retention, baseline patient characteristics, center performance, timeliness of data submission and protocol adherence, withdrawals (in addition to safety and efficacy data). Data will be reported by clinic.

13.5 Study Records Retention

Study records will be maintained for at least three years from the date that the grant federal financial report (FFR) is submitted to the NIAMS. These documents may be retained for a longer period, however, if required by local regulations. No records will be destroyed without the written consent of the sponsor, if applicable. It is the responsibility of the sponsor to inform the investigator when these documents no longer need to be retained.

Statistical Analysis Plan (SAP): Community-based Assessment of Skin Care, Allergies, and Eczema (CASCADE)

i. Administrative information

i.1. Version Information

Trial full title	Community-based Assessment of Skin Care, Allergies, and Eczema (CASCADE)
Trial short title	CASCADE
NIAMS grant number	R01 AR071057
Unique protocol id	00106351 (University of Utah IRB)
ClinicalTrials.gov registration	NCT03409367
SAP version	3.0
SAP version date	April 18, 2023
Senior trial statistician	[name]
Trial statisticians	[name] [name], MS
SAP associated with protocol version	13 (06Jun2021)
Trial principal investigator	[name]

i.2. Revision History

Version 1.1

Justification: Edit plan submitted with funding proposal

Timing: Before analysis, study in progress

Revisions

- Reorganization of text for clarity
- Greater detail provided of variable definitions
- Secondary analysis of ceramide-containing emollients added in response to emerging efficacy evidence

Version 2.0

Justification: Recommendation of DSMB

Timing: Before analysis, study in progress, enrollment complete

Revisions

- Eliminate interim analysis. Revise sample size calculation without alpha spending.
- Add secondary outcome of skin infections (previously appeared in table but not text)
- Add exploratory analyses of bathing and caesarean births as effect modifiers
- Add sensitivity analyses of COVID-19 pandemic effects of potentially changing prevalence of (a) primary outcome and (b) respiratory syncytial virus (RSV) over time.

Version 3.0

Justification: Clarifications in response to questions raised during chart reviews

Timing: Before analysis, study in progress, enrollment complete (April 2023)

Revisions

1. Remove secondary outcome of AD diagnosis by any method (chart, parent report, instruments). Instead, analyze competing definitions using multivariate methods.
2. Add secondary endpoint of cumulative incidence of AD at 18 months. During chart audits (ongoing), research staff have noted that many children have visits in this window who may be missing a visit in the 24-month window.
3. For skin infection secondary endpoints, separate documented physician diagnosis from topical antibiotic prescription.
4. Add pooled logistic regression as an analytic approach for time to diagnosis.

i.3. Signatures

SAP author

[name]

Senior statistician

[name]

Principal Investigator

[name]

ii. List of Abbreviations

AD	Atopic Dermatitis
AE	Adverse Event/Adverse Experience

Atopic dermatitis (AD) affects over 9 million children in the U.S. and ranks first among all skin conditions in global disability burden. Atopic dermatitis often heralds the development of several comorbidities including asthma, food allergy, skin infections and neurodevelopmental disorders. Because of the significant socioeconomic impact of atopic dermatitis and its effect on the quality of life of children and families, there have been decades of research focused on prevention with limited success. Recent advances in cutaneous biology identify epidermal defects and skin barrier dysfunction to be the key initiators of atopic dermatitis and possibly allergic sensitization. Our central hypothesis is that emollient therapy from birth can prevent the development of atopic dermatitis. The current trial has the following specific aims:

Aim 1: Perform a community-based pragmatic randomized controlled trial investigating whether daily full-body emollient application starting in the first 2 months of life prevents atopic dermatitis in a real-world setting.

Aim 2: As an exploratory aim, determine whether a family history of allergic disease and key early life exposures such as pet ownership modify the preventive effect of emollient therapy on atopic dermatitis.

Additional sub-aims include estimating the effect of emollient therapy on age of onset of AD, disease severity, and symptoms predictive of allergic disease further described below.

2. Study Methods

2.1. Trial Design

This study is a parallel-arm pragmatic randomized-control trial. Dyads of a parent or legal guardian ("parent") and a healthy infant ages 0 to 2 months will be enrolled and followed until age 24

months. Intervention dyads will receive specific instructions to apply full-body lipid-rich emollient daily to infants, plus routine skin care advice, and will receive an emollient of their choice mailed to them during study participation. The control group will receive general skin care advice only. Both groups will receive web-based and text message reminders to follow protocol instructions based on their group allocation until the infant reaches 24 months of age.

2.2. Randomization and Blinding

Participants are recruited from primary care practices participating in a consortium of practice-based research networks. Screening occurs through an online instrument hosted on REDCap. After passing screening and giving informed consent to participate in either arm, participants are randomized using a list embedded in REDCap. The randomization list was generated by study statisticians. Allocation is in 1:1 ratio stratified by primary care clinic, to assure balance at each location, as well as history of atopic disease in a first-degree family member¹. Family history of atopy confers an approximate twofold risk of developing AD and may influence participation, adherence and retention as well, so it is important for the two study arms to be balanced on this risk factor.

Neither clinic staff (including primary providers) nor study personnel involved in chart review and analysis are informed of treatment assignment and uninformative labels (e.g. "A" and "B") will be used for the two arms when needed. Study participants are informed that it is not currently known which arm is better for skincare.

In recruitment materials, participants must be willing to be randomized to either arm. Intervention materials provide instructions specific to the randomization arm. Primary care clinicians will be asked to evaluate and document AD status at each well child visit through two years of age without knowledge of intervention status. Study personnel involved in chart review will not have access to participants' arm assignment, and during analysis, we will use generic labels for the two arms ("A," "B") until evaluation of the primary outcomes is completed, and whenever practical thereafter.

Study personnel conducting chart review will be asked whether they became unblinded during the audit process.

2.3. Sample Size and Recruitment Duration

1,250 parent/infant dyads (625 per arm) will be enrolled from 25 community-based family medicine and pediatric practices in four states (Oregon, Colorado, Wisconsin, and North Carolina). All parents/legal guardians, including males and females 18 years of age and older who meet inclusion/exclusion criteria are eligible for study participation. Recruitment is expected to take place over the course of 31 months; the time from start of recruitment until final two-year follow-up on all subjects is five years.

Power for Aim 1. For the purpose of the primary analysis, we include a sufficient number of babies in a 1:1 ratio for the two study arms to provide an overall type I error rate of 0.05 and 80% power to detect a 30% relative reduction in cumulative incidence of AD by two years of age (RR=0.7). In our planning grant, we determined the baseline cumulative incidence of AD in this age group and target clinics at 24%, which is consistent with recent population-based 2-year prevalence in the U.K.¹. Because our trials in high-risk populations of daily vs no emollient have shown reductions of 50%, we assume a more conservative 30% reduction to 16.8%. Using a test of two proportions, a total of 982 babies (491 per arm) are required to detect this difference. Allowing for an approximate 20%

¹ The screening questionnaire includes the question "Has at least one of your baby's blood-related PARENTS, BROTHERS OR SISTERS ever been diagnosed with asthma, eczema (atopic dermatitis) or hay fever (seasonal allergies)?" Strata are split at "Yes" responses vs. "No, or don't know."

loss to follow-up, we plan to enroll 1,250 babies (625 per arm). Sample size calculations were performed using Stata/IC version 16.1.

Power for Aim 2. To determine our power to detect significant interactions, we generated plausible 2x2 tables of risk factors (RFs) and AD for each treatment group that would yield absolute differences in the treatment effect of 0.2, 0.3, and 0.4, taking into consideration the study sample size, overall projected AD and treatment effect, previously published risk of AD for the RF, and prevalence of the RF. We simulated 500 replicates of each scenario using the binomial probabilities from the 2x2 tables and tested for significance of the interaction in a log-binomial (relative risk) model as described below. The power estimates in Table 1 are the proportion of simulated datasets in which the null hypothesis was appropriately rejected.

Table 1. Power to detect plausible interactions in exploratory analyses.

Risk factor (RF)	AD risk	Prev-alence	Tx effect if RF+	Tx effect if RF-	Tx effect DIFF	Power at $\alpha=0.1$
Family history of atopy	2.0	0.50	0.63	0.83	-0.20	0.48
			0.60	0.90	-0.30	0.56
			0.57	0.97	-0.40	0.64
High humidity	0.8	0.44	0.82	0.62	0.20	0.40
			0.89	0.58	0.30	0.52
			0.95	0.54	0.40	0.65
Cat owner	1.0	0.30	0.84	0.64	0.20	0.36
			0.91	0.61	0.30	0.48
			0.98	0.58	0.40	0.60
Dog owner	0.7	0.37	0.84	0.64	0.20	0.36
			0.91	0.61	0.30	0.46
			0.98	0.58	0.40	0.59

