| Study Population | 
From our planning period and recent population-based 2-year prevalence in the U.K., we expect the cumulative incidence of AD in the control to be ~24% at two years of age. To estimate at least 30% relative reduction in AD, we require 1,044 dyads (522 per group) to achieve 80% power for a two-tailed test at the 0.05 level of significance. Allowing for an approximately 20% loss to follow-up, we plan to enroll 1,250 babies (625 per arm).
 
1,250 parent/infant dyads will be enrolled from 35 community-based family medicine and pediatric practices from practice-based research networks (PBRNs) in Colorado, Oregon, North Carolina, and Wisconsin. These PBRNs are part of the Meta-network Research And Learning Center (Meta-LARC). Each clinic will be asked to enroll two or more dyads per month for approximately two years, for a total of 50 dyads per clinic. Enrolled dyads will be representative of the gender, race and ethnicity of patients receiving care in participating clinics.
 
Clinical Site Hubs (practice-based research network, PBRN)
 |

| | |
|---------------------------------------|--|
| | 
 • Oregon Rural Practice-based Research Network – Oregon Health & Science University • State Networks of Colorado Ambulatory Practices & Partners – University of Colorado • Wisconsin Research & Education Network – University of Wisconsin • Duke Primary Care Research Consortium – Duke University |

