10.3 Power and sample size calculations

10.3.1 Power and sample size

10.3.2 Primary Outcome

For the purpose of the primary analysis, we will include a sufficient number of babies in a 1:1 ratio for the two study arms to provide an overall type I error rate of 0.05 and 80% power to detect a 30% relative reduction in cumulative incidence over 2 years (also known as

incidence proportion) of AD (RR=0.7). From our planning grant, we estimated the baseline cumulative incidence of AD in this age group and target clinics at 24% at age 2. The trials in high-risk populations of daily vs no emollient have shown reductions of 50%, we assumed a more conservative 30% reduction to 16.8%. Using the O'Brien-Fleming group sequential spending function approach, a total of 982 infants (491 per arm) are required to detect this difference in proportions. Allowing for an approximate 20% loss to follow-up, we plan to enroll **1,250** dyads (625 per arm). Sample size calculations were performed using Stat/IC version 16.1.

Table 6. Power to detect plausible interactions in exploratory analyses (Aim 2).

| Risk factor | AD risk | Prev-alence | Tx effect if RF+ | Tx effect if RF- | Tx effect DIFF | Power at $\alpha = 0.1$ |
|--------------------|---------|-------------|------------------|------------------|----------------|-------------------------|
| Family hx of atopy | 2.0 | 0.50 | 0.63 | 0.83 | -0.20 | 0.48 |
| | | | 0.60 | 0.90 | -0.30 | 0.56 |
| | | | 0.57 | 0.97 | -0.40 | 0.64 |
| High humidity | 0.8 | 0.44 | 0.82 | 0.62 | 0.20 | 0.40 |
| | | | 0.89 | 0.58 | 0.30 | 0.52 |
| | | | 0.95 | 0.54 | 0.40 | 0.65 |
| Cat owner | 1.0 | 0.30 | 0.84 | 0.64 | 0.20 | 0.36 |
| | | | 0.91 | 0.61 | 0.30 | 0.48 |
| | | | 0.98 | 0.58 | 0.40 | 0.60 |
| Dog owner | 0.7 | 0.37 | 0.84 | 0.64 | 0.20 | 0.36 |
| | | | 0.91 | 0.61 | 0.30 | 0.46 |
| | | | 0.98 | 0.58 | 0.40 | 0.59 |

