10.3.3 Power and sample size for detecting effect modifications

To determine our power to detect significant effect size differences stratified by various baseline variables (interaction) such as sex, race or ethnicity, atopic family history, climate, and pet ownership, we generated plausible 2x2 tables of risk factors (RFs) and AD for each treatment group that would yield absolute differences in the treatment effect of 0.2, 0.3, and 0.4, taking into consideration the study sample size, overall projected AD and treatment effect, previously published risk of AD for the RF, and prevalence of the RF. We simulated 500 replicates of each scenario using the binomial probabilities from the 2x2 tables and tested for significance of the interaction in a log-binomial (relative risk) model as described below. The power estimates in Table 6 are the proportion of simulated datasets in which the null hypothesis was appropriately rejected.

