10.4 Statistical analyses

10.4.1 Analysis of Primary Endpoint

For our primary analysis, we will contrast the risk of diagnosed AD by two years of age for the intervention versus control groups under an intention-to-treat (ITT) assumption, where all subjects will be analyzed according to the group to which they were allocated regardless of adherence or group cross-over, and missing outcome values will be multiply imputed using the expectation-maximization (EM) algorithm.⁷⁸ Model: We will use logistic regression with a treatment variable (intervention=1, control=0) and perform a two-tailed likelihood ratio test of the treatment effect at the overall 0.05 level of significance using an O'Brien-Fleming critical boundary to accommodate one planned interim analysis. Because randomization will have been stratified by clinic and family history of AD in a first-degree relative (yes/no), we will include these variables to avoid overestimation of the p-value.^{79,80} We will estimate the absolute and relative differences between groups as the (1) difference and (2) ratio, respectively, of the average conditional predicted risk for intervention versus controls from the logistic model, calculating standard errors and 95% confidence intervals using the delta method. We will use an inclusive strategy to select variables when imputing the missing outcomes^{77,81} using intervention status and clinic along with parent-reported provider diagnosis, risk factors, and emollient use from electronic survey and text responses, as well as interaction terms found to be significant in Aim 2 (below).

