2.4. Statistical Testing Framework

All statistical tests will be conducted as two-sided tests of inequality. For example, as our primary analysis, we will test the hypothesis that the ratio of the intervention:control proportions, a relative risk (RR) measure, is significantly smaller than 1 with a two-sided test: **RR \neq 1 vs RR = 1**.

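### The interaction powers in SAP Table 1 / Protocol Table 6 do not reproduce at any single sample size, and the protocol's required size and interim plan contradict each other and the SAP

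*SAP*

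**What the plan says.** **Aim 2 (interactions).** SAP 2.3 and Protocol 10.3.3 describe 500 simulated datasets per scenario, generated from assumed 2x2 tables and tested for interaction in a log-binomial model. Both describe the results in the same terms: "The power estimates in Table 1 are the proportion of simulated datasets in which the null hypothesis was appropriately rejected" in the SAP and "The power estimates in Table 6 are the proportion of simulated datasets in which the null hypothesis was appropriately rejected" in the protocol. The printed powers are identical, at alpha 0.1. The SAP's general rule on sidedness is "All statistical tests will be conducted as two-sided tests of inequality", and Protocol 10.4.2 specifies a two-sided Wald test at 0.1. Neither table states its N or prints the cell risks.

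**Aim 1 (primary).** The documents agree on 24% against 16.8%, 80% power and two-sided 0.05, but not on what follows:

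- Protocol synopsis, Study Population: "we require 1,044 dyads (522 per group) to achieve 80% power for a two-tailed test at the 0.05 level of significance".
- Protocol 10.3.2: "Using the O'Brien-Fleming group sequential spending function approach, a total of 982 infants (491 per arm) are required".
- Protocol 10.4.1: the primary test is made "using an O'Brien-Fleming critical boundary to accommodate one planned interim analysis". The synopsis (Study Duration) places that interim at the point where half the participants have completed two-year follow-up.
- SAP 2.3 derives the same 982 from a plain two-proportion test. SAP i.2 (Version 2.0) records: "Eliminate interim analysis. Revise sample size calculation without alpha spending". The current SAP text contains no interim and tests at 0.05 (3.1, 5.3).

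All versions lead to 1,250 enrolled, allowing for about 20% loss.

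**The concern.** The powers in each interaction row rise slowly with the size of the difference. Family history goes only from 0.48 to 0.64 while the difference doubles from 0.2 to 0.4. A Wald test at fixed N should climb faster, which suggests an error in the simulation or the table. Family history matters most: it is a randomization stratum, and SAP 5.2 says a stronger effect there would point to recommending daily emollient only for that group. A null interaction read against nearly 50% power means something different from one read against 27%.

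For the primary endpoint, one required size cannot belong both to a fixed design and to a group-sequential one. A reader holding both documents also cannot tell whether an efficacy interim takes place, or whether the final test is at 0.05 or slightly below it.

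**Working it through.** **1. Primary size**

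Inputs (SAP 2.3): p1 = 0.24, p2 = 0.168, mean 0.204, difference 0.072, z = 1.960 and 0.8416.

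n per arm = [1.960·√(2·0.204·0.796) + 0.8416·√(0.24·0.76 + 0.168·0.832)]² / 0.072² = (1.1170 + 0.4777)² / 0.005184 = 490.5, so 491 per arm and 982 in total. **The plan's 982 reproduces exactly, as a fixed design.** Its power is 80.04%.

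With one look at 50% information:

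| Design | Final z (nominal p) | n per arm | n per arm, continuity-corrected |
|---|---|---|---|
| Fixed | 1.960 (0.050) | 490.5 | 517.9 |
| Classic O'Brien-Fleming, inflation 1.0078 | 1.977 (0.048) | 494.4 | 522.0 |
| Lan-DeMets O'Brien-Fleming-type, spent per side | 1.969 (0.049) | 492.4 | 519.9 |

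The continuity-corrected fixed size is (n/4)·[1 + √(1 + 4/(n·0.072))]² with n = 490.5. The synopsis figure of 522 per group matches the corrected classic O'Brien-Fleming size. That origin is an inference, because the synopsis mentions neither feature. With 491 per arm and the classic boundary, power is 79.7%.

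Attrition: 1,250 × 0.8 = 1,000 evaluable. That covers 982 (982/0.8 = 1,228) but not 1,044 (1,044/0.8 = 1,305). Delivering 1,044 from 1,250 requires loss of at most 1 − 1,044/1,250 = 16.5%.

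**2. Interaction powers**

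The cell risks were reconstructed. The control-arm risk without the factor is q = 0.24 / (prevalence × AD risk + 1 − prevalence). The other cells follow from the row's AD risk and its two treatment RRs. This gives an overall intervention risk of 16.7% to 16.9% in every row, against the planned 16.8%.

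Power = Φ(e − 1.645) + Φ(−e − 1.645), where e = |ln(RR+/RR−)| / √V and V = Σ(1 − p)/(n·p) over the four cells.

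Worked row, family history, 0.63 against 0.83, N = 1,000 (250 per cell):

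- q = 0.24/1.5 = 0.16. Control risks are 0.32 and 0.16; intervention risks are 0.2016 and 0.1328.
- V = 0.0085 + 0.0210 + 0.0158 + 0.0261 = 0.0715, so √V = 0.267.
- e = 0.2757/0.267 = 1.031.
- Power = Φ(−0.614) + Φ(−2.676) = 0.270 + 0.004 = **0.27**, against 0.48 stated.

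All rows, by the same formula (simulation agrees to within about 0.01):

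| Factor | Difference | Stated | N = 982 | N = 1,000 | N = 1,250 | N that would give the stated power |
|---|---|---|---|---|---|---|
| Family history | 0.2 | 0.48 | 0.27 | 0.27 | 0.31 | 2,386 |
| | 0.3 | 0.56 | 0.45 | 0.46 | 0.53 | 1,374 |
| | 0.4 | 0.64 | 0.64 | 0.65 | 0.73 | 982 |
| Humidity | 0.2 | 0.40 | 0.29 | 0.29 | 0.33 | 1,656 |
| | 0.3 | 0.52 | 0.50 | 0.51 | 0.58 | 1,042 |
| | 0.4 | 0.65 | 0.70 | 0.71 | 0.79 | 862 |
| Cat | 0.2 | 0.36 | 0.26 | 0.27 | 0.31 | 1,607 |
| | 0.3 | 0.48 | 0.44 | 0.44 | 0.52 | 1,121 |
| | 0.4 | 0.60 | 0.63 | 0.64 | 0.72 | 910 |
| Dog | 0.2 | 0.36 | 0.26 | 0.26 | 0.30 | 1,680 |
| | 0.3 | 0.46 | 0.43 | 0.43 | 0.50 | 1,099 |
| | 0.4 | 0.59 | 0.61 | 0.62 | 0.70 | 925 |

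The Monte Carlo SE of 500 replicates is at most √(0.25/500) = 0.022, or about 4.4 points at 95%. All four 0.2 rows exceed that at 982, 1,000 and 1,250. In every factor the implied N falls as the difference grows, so no common N exists. The best single N (1,314) still misses by up to 16 points. Alpha 0.05, one-sided 0.1 and other definitions of the baseline risk were searched with N left free; none brought the largest miss below 9 points. The odds-ratio and risk-difference scales did not reproduce the table either.

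**The case against.** - **One cell carries the headline.** This is true. The 20-point excess is family history at 0.2 only. At 982, six of the twelve entries lie within 4.4 points of the recomputed values, and the 0.4 rows are right or slightly conservative. The other three 0.2 rows are still 9 to 11 points high at 1,000 and 5 to 7 points high at 1,250.
- **The simulation's 2x2 tables are not printed, so the recomputation is a reconstruction.** This is also true, and it limits how firmly replacement values can be given. It does not rescue the table: the reconstruction returns the planned intervention risk, and the alternatives tried fit no better than 9 points.
- **Aim 2 is exploratory and openly underpowered.** Protocol 10.4.2 says so, and SAP 5.5 puts magnitude ahead of p-values. No decision rule uses these powers. This lowers the severity but does not make the figures correct.
- **982 is not materially too small.** Agreed. The O'Brien-Fleming increment is under 1%, and the SAP labels 982 correctly. The two documents agree on the number; they differ on the method and the interim. The clash of numbers, 982 against 1,044, is inside the protocol.
- **1,250 may simply be 1,044 × 1.2 = 1,253, rounded.** That is possible, but adding 20% does not offset a 20% loss.
- **Removal of the interim is openly recorded.** It is, in the SAP. The protocol's operative text was not brought into line.

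**Conclusion.** The concern holds. The interaction powers do not follow from the method and inputs stated beside them. They are 9 to 21 points too high at the 0.2 difference with 1,000 evaluable infants, and 5 to 17 points too high with 1,250. They also rise too slowly with effect size to fit any one N. This rests on a 24% overall control risk divided by each row's own AD risk and prevalence, with a two-sided Wald test at 0.1.

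For the primary endpoint, 982 is correct as a fixed-design size and mislabelled in Protocol 10.3.2. The synopsis's 1,044 contradicts it and is not delivered at 20% loss. The protocol still plans an interim and a final threshold of about 0.048 to 0.049, where the SAP has no interim and 0.05. Primary power is essentially intact, so this should be corrected but does not threaten the design.

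**What to change.** 1. Rerun the Aim 2 simulation and restate SAP Table 1 and Protocol Table 6, giving the N used and the cell risks for each row. Under the reconstruction above, the values to expect at 1,000 evaluable infants for differences of 0.2/0.3/0.4 are: family history 0.27/0.46/0.65; humidity 0.29/0.51/0.71; cat 0.27/0.44/0.64; dog 0.26/0.43/0.62. If the sponsor's 2x2 tables differ, print them.
2. In the protocol, remove the interim analysis (synopsis, Study Duration; 10.4.1) and the O'Brien-Fleming wording (10.3.2, 10.4.1). Describe 982 as the fixed two-proportion size, and replace 1,044 (522 per group) in the synopsis with 982 (491 per arm). Size, alpha of 0.05 and the absence of an interim then match the SAP.

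Cost: one simulation rerun, text changes, and the IRB review that Protocol 12.2 requires for any amendment. The Aim 2 powers at the smallest difference become less favourable. Enrolment and the primary analysis in the SAP are unchanged.
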